3.1 General Description

This is an open-labeled study to test the response of a heterologous additional dose with the Janssen Ad26.CoV2.S vaccine in patients who had a poor anti-SARS-CoV-2 spike protein response to mRNA vaccinations. The study includes a randomized trial of the adjustment of immunosuppression on the response to receiving the Janssen Ad26.CoV2.S vaccine.

3.1.1 Segment I

From the screened population, 100 kidney transplant recipients with an anti-SARS-CoV-2 spike protein antibody levels >0 but $<250\text{U/ml}$ (termed low responders) will receive an additional dose of the Janssen Ad26.CoV2.S vaccine. 300 kidney transplant recipients with undetectable anti-SARS-CoV-2 spike protein antibody levels (termed non responders) will receive an additional dose of the Janssen Ad26.CoV2.S vaccine after randomization 1:1 to either a continuation of their current immunosuppression regimen, or after immunosuppression adjustment as defined in Section 5.2.1.

The primary endpoint for Segment I is a SARS-CoV-2 spike protein antibody level $\geq 250\text{ U/ml}$ 28 days after vaccination. Anti- SARS-CoV-2 spike protein antibody levels along with anti-SARS-CoV-2 nucleocapsid antibody levels will be evaluated on days 14, 28, 90 and 180 days. If levels are detectable at Day 180, an additional sample collection will be obtained between one to two years after receiving the Janssen Ad26.CoV2.S vaccine.

- 1) Non-responders (n=300): These are patients who had no antibody response to their initial COVID mRNA vaccination (SARS-CoV-2 spike protein antibody = 0 U /mL). For this randomized portion involving non-responders, we will stratify patients so that we will have equal numbers of patients in each arm who have received 2 doses of mRNA vaccine and equal numbers that have received 3 doses of mRNA vaccine.
 - a. Randomization:
 - i. 150 subjects to receive Janssen Ad26.CoV2.S vaccine.
 - ii. 150 subjects to receive Janssen Ad26.CoV2.S vaccine AFTER immunosuppression adjustment as defined in “Immunosuppression Adjustment” section 5.2.1.
- 2) Low responders (n=100): Patients who had a demonstrable response to COVID mRNA vaccination but were below cutoff (SARS-CoV-2 spike protein antibody 0 to $<250\text{ U/mL}$) will receive the Janssen Ad26.CoV2.S vaccine.

3.1.2 Segment II

In Segment I, 250 subjects will receive the Janssen Ad26.CoV2.S vaccine without immunosuppression adjustment (i.e. they will be maintained on their current immunosuppression). We expect that adjusting immunosuppression increases the response to the Janssen Ad26.CoV2.S vaccine compared to no adjustment. Thus, it is possible that patients from Segment I who were maintained on current immunosuppression, but did respond to receiving the Janssen Ad26.CoV2.S vaccine (i.e. they failed to reach the SARS-CoV-2 spike protein antibody cutoff (≥ 250 U/mL) at 28 days might respond if they underwent immunosuppression adjustment and receive a 2nd vaccination of using the Janssen Ad26.CoV2.S vaccine. A 2nd dose of the Janssen Ad26.CoV2.S vaccine will be offered to these patients. The approach will be similar to Segment I, in that the dose of the Janssen Ad26.CoV2.S vaccine will occur at 2 weeks after immunosuppression adjustment.

The number of patients in this segment could be anywhere between 0 and 250. There is no data to provide an estimate of enrollment, as it can be affected many factors. In prior studies of the mRNA vaccine, most of the low responders developed high levels of antibody after revaccination. If 50% of the non-responders are included here (n=75) and 25 low responders, then the number of subjects receiving the Janssen Ad26.COV2.S vaccine in Segment II would be 100.

Clinical follow-up will be for two years after receiving the Janssen Ad26.CoV2.S vaccine and analysis will focus on transplant specific outcomes (graft and patient survival, rejection episodes, etc.), general health outcomes (incidence of new diagnoses) and COVID specific outcomes (incidence of *de novo* SARS-CoV2 infection and clinical course/outcome).

3.1.3 Responders to mRNA Vaccination

Those participants who were determined to have an initial response to either the Pfizer or Moderna vaccine series (defined as having a screening SARS-CoV-2 spike protein antibody result ≥ 250 U/mL) will not be offered the Janssen Ad26.CoV2.S vaccine. Participants will continue to be followed for approximately 2 years so their information can be used as a comparison for Segments I and II. These participants will be followed for 2 years for clinical outcomes (COVID infections, graft and patient survival). During this time their medical information will be collected, both through medical chart review and by the study team, and Mechanistic Studies will be performed (in a subset of subjects).

3.1.4 Exploratory Mechanistic Immunologic Studies

The immunologic mechanisms associated with a poor anti-spike protein antibody response after vaccination have not been studied in detail. We plan to explore the causes through a battery of immunologic assays. These detailed studies of T and B cells will be performed in a subset of patients to determine if specific alterations in immunity correlate with poor responsiveness to vaccination.

The following patients will have blood drawn for immunologic assays:

- 1) Initial responders (n=50):

- a. Patients who during screening have anti-SARS-CoV-2 spike protein antibody levels ≥ 250 ; one time point.
- 2) Low responders (n=50):
 - a. Patients who are low responders (anti-SARS-CoV-2 spike protein antibody >0 , but less than 250 U/ml) at screening.
- 3) Non-responders (n=50) with no change in immunosuppression:
 - a. Patients who have no detectable anti-SARS-CoV-2 spike protein antibody that are randomized to remain on their current immunosuppression.
- 4) Non-responders (n=50) with a reduction in immunosuppression:
 - a. Patients who have no detectable anti-SARS-CoV-2 spike protein antibody that are randomized to the immunosuppression adjustment arm.
 - b. Unlike the other patient groups, these subjects will have blood drawn for immunologic assessments at two time points; one prior to adjustment in their immunosuppression and a second performed 2 weeks after their immunosuppression is adjusted, but prior to receiving the Janssen Ad26.CoV2.S vaccine. This is intended to document any changes in immunologic profile secondary to immunosuppression adjustment.

Note, the immunologic assays will not be used for patient management or for decision-making in the trial. Thus, assays will be performed over the entire enrollment period until the target number of assays are performed. Patients receiving the Janssen Ad26.CoV2.S vaccine in Segment I will have anti-SARS-CoV-2 memory B cells and anti-SARS-CoV-2 T cell assays performed before and after vaccination. In addition to the tests described above, additional blood samples will be collected and stored for future testing. The details of the future tests will be outlined in a subsequent protocol amendment. The stored blood samples will not be analyzed until the protocol amendment is approved by the IRB.

Exploratory Mechanistic Study Lab Assessments.

The table below details the timing of each mechanistic study assay for each patient group but may not be limited to those studies included on the list. Samples will be collected as close to the timepoint as possible, but some variation is expected and will not be considered a deviation. All these studies will be performed on peripheral blood. These assays will be performed in multiple laboratories located at Mayo Clinic Rochester or in Rochester, Minnesota.

Only a subset of subjects in each group will be included in the mechanistic studies. Subjects will be selected based on their availability to have blood drawn. In the initial responder group 50/800 subjects will have blood drawn on the day of a routine clinic visit. The remaining subject groups will have blood drawn prior to and post-vaccination on 50 unique subjects from each group (see table below).

Mechanistic study	Initial responders (n=50) ANY visit	Low responders (n=50)			Non-responders (No Immuno change; n=50)			Non-responders (Immuno change; n=50)			
		Day 0	Day 28	Day 1-2 yrs	Day 0	Day 28	Day 1-2 yrs	Day -14	Day 0	Day 28	Day 1-2 yrs
Total Immunoglobulin levels	X	X			X			X	X		
T-cell immunophenotyping	X	X			X			X	X		
B-cell immunophenotyping	X	X			X			X	X		
Covid T-cell ELISPOT	X	X	X		X	X			X	X	
Covid Memory B-cell	X	X	X		X	X			X	X	
Neutralizing antibody	X	X	X		X	X			X	X	
T-cell repertoire (spectratyping)	X		X			X		X		X	

Note: Subjects enrolled in Segment I who end up in Segment II will not have the 1-2 year mechanistic study specimens collected. Once subjects are enrolled in Segment II, they will not have mechanistic studies.

1. Total Immunoglobulin Levels:

- a. Total serum immunoglobulin levels – IgG, IgA and IgM will be tested.
- b. Samples will be collected prior to vaccination (Day 0) in all groups receiving vaccination and in the group receiving reduced immunosuppression prior to immunosuppression reduction (Day -14).
- c. These assays will be performed in the Protein Immunology Laboratory at Mayo Clinic Rochester (clinical lab).

2. T-cell and B-cell Immunophenotyping:

- a. Flow cytometric analysis using pertinent cell markers: CD3, CD8, CD4, CD20, CD38, CD27, IgD, Ki67. This will determine total T cells, T helper cells and CD8 T cells and naïve B cells, memory B cells, plasmablasts and plasma cells.
- b. Samples will be collected prior to vaccination (Day 0) in all groups receiving vaccination and in the group receiving reduced immunosuppression prior to immunosuppression reduction (Day -14).
- c. These assays will be performed in the Cellular and Molecular Immunology Laboratory in the Mayo Clinic Rochester Campus (Directed by [name]).

3. SARS-CoV-2 T-cell ELISPOT:

- a. This assay tests for T-cell activation when exposed to COVID spike protein.
- b. Samples will be collected prior to vaccination (Day 0) in all groups receiving vaccination and at Day 28 (post-vaccination).
- c. These assays will be performed in the Cellular and Molecular Immunology Laboratory in the Mayo Clinic Rochester Campus (Directed by [name]).

4. SARS-CoV-2 Memory B-cell:

- a. Flow-cytometric assay that measures the percentage of memory B cells that bind SARS-CoV-2 -spike protein (flourochrome labeled).
- b. Samples will be collected prior to vaccination (Day 0) in all groups receiving vaccination and at Day 28 (post-vaccination).
- c. These assays will be performed in [name] research laboratory located on the Mayo Clinic Rochester campus.

5. Neutralizing antibodies:

- a. This assay quantifies the SARS-CoV-2 virus neutralizing antibodies.

- b. Samples will be collected prior to vaccination (Day 0) in all groups receiving vaccination and at Day 28 (post-vaccination).
 - c. These assays will be performed at Imanis Life Sciences (Rochester, MN).
6. T cell repertoire:
 - a. This is a PCR assay that determines the number and type of T cell receptors present in a population of cells.
 - b. Samples will be collected from Day 0 to 1-2 years in the Low Responder and Non-Responder groups. Samples will be collected in the Initial Responder group at any visit. In addition, the immunosuppression reduction group will have a specimen processed at the time of immunosuppression reduction (Day -14).
 - c. These assays will be performed in the Cellular and Molecular Immunology Laboratory in the Mayo Clinic Rochester Campus (Directed by [name]).

The study team has been in contact with all included laboratories. All labs have agreed to participate in the study **AND** have the capacity to complete the study as designed. Whenever possible, residual specimens will be stored in [name] research laboratory for future use. The [name] laboratory is equipped with multiple large cryogenic tanks, 5 – 20 ft³ supercold (-80°) freezers and sample tracking methods suitable for long-term sample storage.

3.1.5 Study Measurements

The following are the study measurements to be obtained in this clinical trial:

- Roche anti-SARS-CoV-2 spike antibody testing will be performed prior to receiving the Janssen Ad26.CoV2.S vaccine
 - These tests will be performed at Mayo Clinic Rochester using specimen kits mailed in or on specimens collected at the study site.
 - The data from the 28 day measurement will be used as primary endpoint. The other measurements will be used to assess the response to the Janssen Ad26.CoV2.S vaccine early (post - 14 days) and late (post - 90 to 180 days). If levels are detectable at Day 180, an additional sample collection will be obtained from one to two years.
- Anti-SARS-CoV-2 nucleocapsid total antibody testing will be performed at the same time as the anti-SARS-CoV-2 spike protein testing.
 - This assay is intended for use as an aid in identifying individuals with an adaptive immune response to SARS-CoV-2 virus, indicating recent or prior infection.
 - These assays will be performed in the Central Clinical Laboratory in the Mayo Clinic Rochester campus.
- Clinical data:
 - Mayo Clinic Transplant utilizes the "Phoenix" module for EPIC to capture Transplant Specific information.
 - This will be used to collect all relevant clinical information including patient demographics, patient and graft status, adverse events, follow-up, etc.
- Study data:

- Study specific data (labs, study diary, adverse events, etc.) will be entered into a RAVE database that can be easily interfaced with the EPIC (Phoenix [Transplant] and Healthy Planet [COVID]) databases.
- Mechanistic studies (Section 3.1.4)

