3.4 Primary Study Endpoints

The primary endpoint of all studies is the detection of antiSARS-CoV-2 spike antibody levels ≥ 250 U/ml in serum 28 days after receiving the Janssen Ad26.CoV2.

We have dual primary objectives in this study with the response defined as the following: achieving an anti-SARS-CoV-2 spike protein antibody level ≥ 250 U/ml 28 days after an additional dose with the Janssen Ad26.CoV2.S vaccine.

1. To assess whether an anti-SARS-CoV-2 spike protein antibody level of ≥ 250 U/mL can be achieved 28 days after a dose of the Janssen Ad26.CoV2.S vaccine in kidney transplant recipients who did not form acceptable levels of anti-SARS-CoV-2 spike protein antibody (<250 U/ml but >0 U/mL) after receiving two or more doses of a mRNA vaccine: Pfizer-BioNTech (BNT162b2 vaccine) or Modena (mRNA-1273). This includes any combination of the Pfizer-BioNTech (BNT162b2 vaccine) or the Moderna (mRNA-1273) results in two or more doses of mRNA vaccine. This is not randomized and not controlled.
2. To compare whether a dose of the Janssen Ad26.CoV2.S vaccine can achieve an anti-SARS-CoV-2 spike protein level ≥ 250 U/mL in kidney transplant recipients with no detectable anti-SARS-CoV-2 spike protein antibody after two or more mRNA vaccines. Kidney transplant recipients will be randomized to either maintenance of current immunosuppression or

adjustment in immunosuppression around the time of receiving the Janssen Ad26.CoV2.S vaccine. The number of subjects with anti-SARS-CoV-2 spike protein level ≥ 250 U/mL between the two randomized groups will be compared.

Thus, the ***primary comparison*** for this study is the rate of achieving this endpoint after receiving the Janssen Ad26.CoV2.S vaccine in patients who: 1) had undetectable anti-SARS-CoV-2 spike protein antibody levels after 2 or more doses of mRNA vaccine; and then were 2) randomized to either no alteration in immunosuppression vs alteration in immunosuppression around the time of receiving the Janssen Ad26.CoV2.S vaccine. The power calculations will focus on the difference in the proportion of patients who meet this endpoint between those with no alteration and those with an alteration in immunosuppression.

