6.2 Segment II

This segment will be evaluating the dosing of the Janssen Ad26.COv2.S vaccine with immunosuppression adjustment of patients in Segment I who were maintained on their current immunosuppression and had a lack of response at Day 28. Lack of response for this study is defined as anti-SARS-CoV-2 spike protein levels <250 U/mL.

Study procedures for Segment II will proceed in the same manner and schedule as in Segment I with the absence of screening procedures and mechanistic studies excluding the anti-SARS-CoV-2 Nucleocapsid Total Antibody test. Samples collected for the anti-SARS-CoV-2 Nucleocapsid Total Antibody test will continue to be obtained and will align with the collection and timepoints noted for the anti-SARS-CoV-2 spike protein antibody test. As all subjects will experience a reduction in IS, the Nephrologist will confirm medication compliance with the adjusted IS regimen during the Nephrology consult prior to receiving the Janssen Ad26.CoV2.S on Day 56. See Schedule of Events 3: Segment II in Section 6.6 for more details on study procedures.

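### The durability analysis has no rule for infection after enrolment, although nucleocapsid antibody is drawn alongside spike to detect it

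*Combined protocol and SAP*

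**What the plan says.** **Collection.** Section 3.1.5 states: "Anti-SARS-CoV-2 nucleocapsid total antibody testing will be performed at the same time as the anti-SARS-CoV-2 spike protein testing". It gives the purpose as helping to recognise people who have mounted an immune response to the virus, "indicating recent or prior infection". For Segment I, Section 3.1.1 says spike levels "along with anti-SARS-CoV-2 nucleocapsid antibody levels will be evaluated on days 14, 28, 90 and 180 days". Sections 6.1.1 and 6.1.3 add screening and Day 0, and Section 6.1.7 adds Year 1 for patients with detectable antibody at Day 180. In Segment II the nucleocapsid samples "will align with the collection and timepoints noted for the anti-SARS-CoV-2 spike protein antibody test" (Section 6.2).

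**Endpoints and analysis.** Section 3.4 defines response as "achieving an anti-SARS-CoV-2 spike protein antibody level ≥ 250 U/ml 28 days after an additional dose with the Janssen Ad26.CoV2.S vaccine", with no condition on infection. Section 3.5 defines durability as spike levels at 180 days and/or between 1 and 2 years in patients who developed any antibody response. Section 6.8 specifies a chi-square test for the randomised comparison and mixed effects models for durability. Neither Section 6.8 nor the populations in Section 6.9 mention nucleocapsid antibody or a rule for infection.

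**Infected patients stay in the data.** Prior infection is not an exclusion (Section 4.2). Under Section 7.5, a molecularly confirmed infection on study samples stops further study doses, but the patient remains in immunogenicity follow-up. The infection outcome comes from a registry of clinical diagnoses and positive PCR results (Section 8.5). The schedules in Section 6.6 have no PCR row.

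**The concern.** The vaccine encodes the spike protein (Section 5.1), so a spike level alone cannot show whether a rise came from the vaccine or from the virus. The paired nucleocapsid test is the plan's only scheduled laboratory check for an infection that nobody reported, yet the stated analyses give its results no role after enrolment.

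Durability is where this bites. A patient whose vaccine antibody has waned, and who is then infected, contributes a high value at Day 90, Day 180 or Year 1, and the mixed model treats it as persistence. The Year 1 rule adds to this: because that draw requires detectable antibody at Day 180, an infection before Day 180 can itself bring a waned patient into the Year 1 sample. The durability estimate would then mix persistence of vaccine antibody with the course of the epidemic.

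The same mechanism could in principle add responders at Day 28 in Segment I and Day 84 in Segment II, so its size there also needs checking.

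**Working it through.** **Inputs.** Infection rate of about 10% per year, described as from before vaccination programmes (Section 6.8, note on COVID-19 incidence). Response rates of 20% vs 37%, 150 per arm, two-sided alpha 0.05, arcsine scale (Section 6.7). Low responders: 60%, and elsewhere more than 90 of 100 (Section 6.7). Segment II: 60% (Section 6.7). The rates of 20% and 40% per year below are assumptions, used because the plan calls the future rate unknown.

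**The plan's power figure.** h = 2·asin(√0.37) − 2·asin(√0.20) = 1.308 − 0.927 = 0.380. Power = Φ(0.380 × √75 − 1.96) = Φ(1.335) = 0.909. The stated 90% reproduces.

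**Share infected by day d** at annual rate r: q = 1 − (1 − r)^(d/365.25).

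| Interval | 10% per year | 20% (assumed) | 40% (assumed) |
|---|---|---|---|
| 28 days (Day 0 to 28) | 0.8% | 1.7% | 3.8% |
| 49 days (Day −21 to 28) | 1.4% | 3.0% | 6.6% |
| 56 days (Day 28 to 84, Segment II) | 1.6% | 3.4% | 7.5% |
| 180 days | 5.1% | 10.4% | 22.3% |
| 365 days | 10.0% | 20.0% | 40.0% |

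**Durability.** At 10% per year, of 400 vaccinated patients, 400 × 0.0506 = 20 would be infected by Day 180 and 400 × 0.0999 = 40 by Year 1. The durability set is smaller than 400, but the percentages carry over if its infection rate is the same. At the late edge of the visit windows (Day 210, Day 425) the shares are 5.9% and 11.5%. All of these are shares infected. They bound the share of contaminated values, because an infection need not raise spike.

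**Day 28 response.** Infection changes the result only for a patient who would otherwise miss 250 U/mL and whom it lifts to that level. The inflation is therefore at most (1 − p) × q. With q = 1.4%:

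- No adjustment, p = 20%: 0.80 × 1.4 = 1.1 points, giving 21.1%.
- Adjustment, p = 37%: 0.63 × 1.4 = 0.9 points, giving 37.9%.
- Difference: it shrinks by (0.37 − 0.20) × 1.4 = 0.24 points, toward the null, if infection is equal by arm.
- Low responders: 0.40 × 1.4 = 0.56 points at p = 60%; 0.10 × 1.4 = 0.14 points at p = 90%.
- Segment II, p = 60%: 0.40 × 1.4 = 0.56 points over 49 days; 0.40 × 1.6 = 0.64 points over the 56 days from Day 28 to Day 84.

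If every infection counted as a response, power for 20% vs 37% would fall from 0.909 to 0.901 over 28 days of exposure and to 0.893 over 56 days. At the assumed 20% and 40% per year, over 28 days, it would be 0.892 and 0.868.

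**The case against.** **Nucleocapsid status may be used at baseline.** A reader might infer that no analysis uses the assay at all. The documents do not support that. Section 6.8 promises descriptive summaries of all variables, including baseline values, by treatment group and antibody stratum, compared for possible confounding. It also promises logistic models of response on possible confounders. Baseline nucleocapsid status fits that wording, though it is not named. What is missing is a rule for infection after enrolment, and those summaries do not alter the durability model.

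**Day 28 is hardly touched.** This stands. A reader might infer that the primary comparison is compromised, especially if infection differs by arm under reduced immunosuppression or open-label behaviour. The plan gives no figure for such a difference, so that remains conjecture.

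**The remark about a 1–2% response rate.** Section 6.7 says such a rate would be statistically significant for the uncontrolled primary objective, and a reader might infer that infection alone (0.8% to 1.4%) could deliver success. The remark serves only to explain why power was not calculated. The benchmarks the plan calls clinically meaningful are above 50% for low responders and 20% for non-responders on current immunosuppression. Inflation of about 0.1 to 0.6 points for low responders, or 1.1 points for those non-responders, is small against them.

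**The marker is imperfect.** Section 3.1.5 calls it an aid. Patients selected for making no spike antibody may also fail to make nucleocapsid antibody, and that could depend on the immunosuppression arm. Censoring may be informative if low antibody predicts infection. Counting every seroconverter as a failure would also mislabel a patient who reached 250 U/mL before being infected. Analysing all antibody values regardless of infection is a legitimate choice if it is stated. These points shape the remedy; they do not remove the gap.

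**Conclusion.** The gap is real and minor, and it matters mainly for durability. Without an infection rule, the mixed model counts infection-driven spike rises as persisting vaccine antibody. At the plan's 10% per year this affects at most about 5% of vaccinated patients by Day 180 and 10% by Year 1. At assumed rates of 20% to 40% per year, the bounds are 10% to 22% and 20% to 40%.

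At 10% per year the effect on Day 28 response is at most about 1 point per arm and about 0.2 points on the randomised difference. For low responders and Segment II it is about 0.1 to 0.6 points. These figures assume a constant rate, nominal visit days, equal infection by arm, and that every infection takes spike to 250 U/mL or above. The last assumption makes them upper bounds at the stated rate. They give no reason to doubt the primary test or the low-responder conclusion.

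**What to change.** 1. **Durability.** Specify that the main model excludes spike values after first evidence of infection: nucleocapsid seroconversion, positive PCR or clinical COVID-19 diagnosis. Report the model on all values beside it, because censoring may be informative and seroconversion may be less sensitive under immunosuppression.
2. **Primary test.** Leave the chi-square test unchanged.
3. **Sensitivity analysis of response at Day 28, and at Day 84 in Segment II.** Treat patients infected between the qualifying spike test (screening in Segment I, Day 28 in Segment II) and the endpoint draw as non-responders. The exception is a patient who already had spike ≥250 U/mL after vaccination and before evidence of infection. Show results by baseline nucleocapsid status as well.

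No new samples, visits or patients are needed. The cost is SAP wording, slightly fewer late spike values in the main durability model, and a little more programming. Because the trial is open label, the rule is best fixed before post-vaccination antibody data are examined.
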